## 10.0 Statistical Considerations

This is a pilot trial investigating three doses of CPI-613 (500, 1500, and 2,000 mg/m^2). We plan to accrue between 10 and 15 patients per year for a total of 67 patients (20 at 500, 1,500 mg/m^2 and 3 additional patients at 2,000 mg/m^2). Of note 17 patients at 2,000 mg/m^2 and 7 patients at 2,500 mg/m^2 were already accrued.

### Analysis Plan:

The primary objective of determining the feasibility of administering CPI-613 in combination with high dose cytarabine and mitoxantrone during induction, consolidation and maintenance therapies will be completed by determining the percentage of patients eligible for maintenance therapy who complete at least 3 cycles. If  $\geq 50\%$  of eligible patients complete 3 cycles of maintenance therapy we will consider this regimen feasible for future study. Given an estimated response rate of 50% and a 25% attrition to stem cell transplant, if we enroll 60 patients we should be able to assess feasibility of maintenance in approximately 22 patients. With 22 evaluable patients, a two-sided 95.0% confidence interval using the large sample normal approximation will extend 22% in either direction from the observed value when the expected value is 50%. Within a dose we should be able to estimate feasibility in 7 patients with a 95% confidence interval extending 36% in either direction.

Participants will also be followed and analyzed for secondary outcomes of response rate and overall survival both overall and by dose. Participants will be monitored for survival through routine follow-up visits. Confidence intervals will be calculated around the estimates of the response rate (CR and CRi). Assuming a response rate of 0.5, with 60 participants, we would be able to create 95 percent confidence intervals with a 0.13 margin of error (0.37, 0.63). We will use Kaplan-Meier estimation to analyze overall survival. The frequency of toxicities experienced by the participants will be presented by type and grade in an effort to monitor and report safety of the treatment.

In exploratory analysis we plan to compare both complete response and early mortality (death within 60 days of beginning of treatment) to the observed rates in a historical cohort of subjects (CCCFWFU 22111), both overall and by dose. In the historical cohort the response rate was estimated to be 41%. Using a one-sided chi-square test, a 0.05 significance level, null hypothesis of 41%, and assuming 70% power, we would be able to show significant improvement in response if we are able to achieve a response rate of 56% or higher. Early mortality in the historical cohort was estimated to be 29% at 60 days. We will use a one-sided exact test for a single proportion, a 0.05 significance level, a null hypothesis of 29%, and 70% power. To show a significant decrease in early mortality in this study we would need to observe a 60 day mortality rate of 16.8% or lower.

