## SCHEMA

This is a Pilot open label trial to establish the feasibility of CPI-613 in combination with high dose cytarabine and mitoxantrone:

*Salvage Induction:* CPI-613 at doses of 1,500 mg/m^2/day will be given over 2 hours on days 1-5. Cytarabine will be given at 3gm/m^2 for age <60 or 1.5 gm/m^2 for age >60 in 500 mL NS over 3 hours every 12 hours for 5 doses starting on day 3. Mitoxantrone will be given at 6mg/m^2 daily for 3 doses given in 50 mL NS over 15 minutes after 1st, 3rd and 5th doses of Cytarabine. A day 14 marrow will be obtained to assess disease response. If there is a response to therapy but residual disease remains patients may receive either a repeated courses identical to the above or a shortened 3 day course with CPI-613 on days 1-3, cytarabine starting on day 2 for 3 total doses and Mitoxantrone after 1st and 3rd doses at the discretion of the treating physician.

There will be 20 patients recruited at a CPI-613 dose of 500mg/m^2/day following the same treatment guidelines outlined above. Individuals recruited to this dose level of CPI-613 will remain on this dose level for consolidation and maintenance therapy.

*Salvage Consolidation:* All responding patients are eligible for consolidation therapy with up to 2 cycles of the shortened 3 course of CPI-613 (same dose as induction cycle), high dose cytarabine and mitoxantrone. Responding patients can be removed from trial at any time to receive a stem cell transplant at the discretion of the treating physician. Patients can move to maintenance following 1, 2 or no cycles of consolidation at the discretion of the treating physician.

*Maintenance Therapy:* Any patient who has completed all planned consolidation therapy (i.e. 0, 1 or 2 cycles) and is not eligible for, faces a significant delay or refuses a stem cell transplant may receive maintenance therapy with CPI-613 at a dose of 2,500 mg/m^2/day over 2 hours on days 1-5 of a 28 day cycle. Patients treated during induction and consolidation at the 500 mg/m^2 dose will receive that dose during maintenance therapy. Patients may continue on maintenance therapy until evidence of disease progression or occurrence of intolerable side effects.

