## 4.0 Registration Procedures

All patients entered on any CCCWFU trial, whether treatment, companion, or cancer control trial, **must** be linked to the study in EPIC within 24 hours of Informed Consent. Patients **must** be registered prior to the initiation of treatment.

You must perform the following steps in order to ensure prompt registration of your patient:

1. Complete the Eligibility Checklist (Appendix A)
2. Complete the Protocol Registration Form (Appendix B)
3. Alert the Cancer Center registrar by phone, *and then* send the signed Informed Consent Form, Eligibility Checklist and Protocol Registration Form to the registrar, either by fax or e-mail.

Contact Information:

Protocol Registrar [contact]

Protocol Registrar [contact]

Protocol Registrar E-MAIL ([[contact]](mailto:[contact]))

\*Protocol Registration is open from 8:30 AM - 4:00 PM, Monday-Friday.

4. Fax/e-mail ALL eligibility source documents with registration. Patients **will not** be registered without all required supporting documents.

Note: If labs were performed at an outside institution, provide a printout of the results. Ensure that the most recent lab values are sent.

To complete the registration process, the Registrar will:

- assign a patient study number
- assign the patient a dose
- register the patient on the study

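### The named normal approximation gives 21%, not 22%, for 22 evaluable patients (the method label may be at fault), and the total of 67 includes three patients at a dose that the treatment plan and registration form do not offer

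*Combined protocol and SAP*

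**What the plan says.** The Analysis Plan in Section 10.0 assumes a 50% response rate and 25% attrition to transplant, and concludes that "if we enroll 60 patients we should be able to assess feasibility of maintenance in approximately 22 patients". For those 22 patients, at an expected value of 50%, it states that "a two-sided 95.0% confidence interval using the large sample normal approximation will extend 22% in either direction". It continues: "Within a dose we should be able to estimate feasibility in 7 patients with a 95% confidence interval extending 36% in either direction". For the response rate, with 60 participants, it gives a margin of 0.13 (0.37 to 0.63). The regimen counts as feasible if at least 50% of patients eligible for maintenance complete three cycles.

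The opening of Section 10.0 gives a total of 67 patients: 20 at 500 mg/m², 20 at 1,500 mg/m² and "3 additional patients at 2,000" mg/m², with 17 at 2,000 mg/m² already in. It adds that "7 patients at 2,500 mg/m 2 were already accrued".

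Elsewhere, new patients have two doses. The Schema says "CPI-613 at doses of 1,500 mg/m 2 /day will be given over 2 hours on days 1-5" and "There will be 20 patients recruited at a CPI-613 dose of 500mg/m 2 /day". Section 5.0 gives 500 or 1,500 mg/m² for induction and consolidation. Section 5.3 gives the same two doses and mentions 2,000 mg/m² only as 17 patients already accrued. Under Section 4.0 the registrar will "assign the patient a dose", and the dose line of the Protocol Registration Form in Appendix A lists only 500 and 1,500 mg/m².

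**The concern.** The plan fixes every input to the 22%: number of patients, expected proportion, confidence level and method. A reader who applies them does not get 22%. This is the overall precision statement for the primary endpoint, so method and figure should agree, not least because the method named is the one an analyst would use for the final interval.

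The accrual point is separate and is not an addition error. Section 10.0 counts on three more patients at a dose that the treatment plan does not provide for and that the form cannot record. The planned total therefore depends on which part of the protocol is followed.

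**Working it through.** **Evaluable patients** (inputs from the Analysis Plan). Enrolled × 0.50 × 0.75:

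- 60 enrolled: 22.5, which the plan gives as about 22.
- 20 in a dose cohort: 7.5, which the plan gives as 7.

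**Normal approximation**, half-width = 1.96 × √(0.25/n), against the exact (Clopper-Pearson) half-width:

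| Figure | Stated | Normal | Exact |
|---|---|---|---|
| Overall, n = 22 | 22% | 20.9% | 21.8% |
| Per dose, n = 7 | 36% | 37.0% | about 36% |
| Response, n = 60 | 0.13 | 12.7% | 13.2% |

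The response margin is reproduced by either method. The 22% is not reproduced by the named method, and the 36% is not reproduced by it at 7 patients.

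**Can rounding or another enrolment total rescue the 22%?**

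- The normal half-width rounds to 22% only for n between 18.97 and 20.78, that is, 19 or 20 patients.
- The unrounded 22.5 gives 20.7%, which is further away.
- Enrolment of 57, 64 or 67 gives 21.4, 24.0 or 25.1 evaluable, and 21.2%, 20.0% or 19.6%.

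So no enrolment total supported by the documents gives 22%. The 36% differs: at the unrounded 7.5 the normal approximation gives 35.8%.

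**Which other method fits?** A t interval gives 22.2% at n = 22 but 46.2% at n = 7, so it fails the second figure. The exact interval fits all three:

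- 11/22: 28.2% to 71.8%, half-width 21.8%.
- n = 7: half of 7 is not a whole number. The formula evaluated at 3.5 gives 36.1%. At 3/7 the limits are 9.9% to 81.6%, about 33 points down and 39 up, an average of about 36%.
- n = 60 at 50%: 13.2%.

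**Accrual.** 20 + 20 + 3 + 17 + 7 = 67. Without the three, 67 − 3 = 64.

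The Analysis Plan does not itemise its 60. Assume it is three cohorts of 20, with the 2,000 mg/m² cohort made up of 17 + 3. Without the three:

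- Overall: 57 enrolled and 57 × 0.375 = 21.4 evaluable instead of 22.5. The normal half-width moves from 20.7% to 21.2% (unrounded n).
- The 2,000 mg/m² cohort: 17 × 0.375 = 6.4 evaluable instead of 7.5. The normal half-width moves from 35.8% to 38.8% (unrounded), or from 37.0% to 40.0% (7 against 6 patients).
- Response margin: 0.1298 at 57 against 0.1265 at 60, so still 0.13.

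**The case against.** The strongest reply is that nothing turns on the 22%. It is a planning statement attached to an approximate count, it differs by about one point (the equivalent of 20 patients against 22), and it claims less precision than the named method delivers. The feasibility rule uses the point estimate, and no sample size or test depends on the half-width. All of that stands, and it keeps the point minor. It does not make the figure and its label agree.

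A reader might infer that 22% is simply a wrong number. The documents do not support that, because the exact interval matches all three stated figures and the label may be what is wrong. Nor do they prove that the exact interval was used: they show no calculation, and a slip is also possible. It would likewise be too strong to call the 36% a second definite error, because the named method reaches it at 7.5.

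On accrual, it is fair to say that 67 is added correctly and that the Schema conflicts with Section 10.0 only by having no 2,000 mg/m² entry. Sections 5.0 and 5.3 and the registration form carry the contradiction. A reader might also infer that the 60 in the Analysis Plan must fall to 57. That holds only if the 60 includes the three, which the plan does not say.

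**Conclusion.** Both parts hold, and both are small.

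The stated 22% does not follow from the stated method, which gives 20.9%. At the stated 7 patients per dose the same method gives 37.0% against 36%. Either the label or the figures should change, and the documents do not settle which. The discrepancy is about one percentage point and leaves the feasibility decision as it is.

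Section 10.0 contradicts the treatment plan and the registration form over three further patients at 2,000 mg/m². Planned accrual is 67 or 64 depending on the passage followed. Any effect on precision rests on the assumption that the 60 is three cohorts of 20: about half a point overall and about three points in the 2,000 mg/m² cohort. Which dose plan is right is not a question for this review.

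**What to change.** For the precision statement, take one of two routes:

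- Name the exact (Clopper-Pearson) interval and keep 22%, giving the limits for 11/22 (28.2% to 71.8%). By dose, replace the symmetric wording with actual limits (for example 3/7: 9.9% to 81.6%) or with an average half-width of about 36%, since that interval is asymmetric.
- Keep the normal approximation and restate 22% as 21%. In the same edit, restate 36% as 37% for 7 patients, or give 7.5 patients for the 36%. Changing only the first figure would leave the same mismatch in the next sentence.

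For accrual, reconcile Section 10.0 with the Schema, Sections 5.0 and 5.3 and the registration form on whether any more patients enter at 2,000 mg/m², and state how the 60 is made up. If the three enter, the total stays 67 and the other passages and the form must agree with it. If they do not, the total is 64; and if the 60 includes them, it becomes 57, with about 21 evaluable overall and about 6 in that cohort.

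The cost is one method label with its by-dose wording, or one or two figures, plus either the accrual totals or the wording of the Schema, treatment plan and form. No extra patients are needed.

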**1.4 Rationale**

Chemotherapy resistance is a major cause of death in patients with relapsed or refractory AML. CPI-613 can increase the sensitivity of leukemia cells to chemotherapy in petri dishes and mice. As a single agent in a phase I clinical trial several relapsed/refractory AML patients had an objective response. Additionally, a phase I study of CPI-613 in combination with high dose cytarabine and mitoxantrone has recently been completed. This trial established the MTD of CPI-613 as 2,500 mg/m^2. Preliminary analysis of the study revealed an overall complete remission or complete remission with incomplete count recovery rate of 45%. This compares favorably with our historical experience of this regimen without CPI-613. In this trial patients with poor risk cytogenetics had a 46% response rate, far superior to the 19% response seen with historical data. This trial established that CPI-613 can be safely administered at 2,500 mg/m^2 in this combination and results in superior response rates. The novel mechanism of action, non-cross resistance with chemotherapeutic agents, lack of CPI-613-related myelosuppression clinically and increase response rate make this regimen a suitable candidate for the proposed pilot study.

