**CYTOGENETICS:**

**Cytogenetics at Diagnosis:**

**Date of Cytogenetics Report:** \_\_\_\_ / \_\_\_\_ / \_\_\_\_

**Risk Category:**  Good  Intermediate  Poor  Unknown  Not Done

\*Enter descriptive text from Cytogenetic Report (3 categories) into REDCap database on Pre-Study Data Collection Form.

CCCFWFU 22215

Comprehensive Cancer Center of Wake Forest University

An Open Label Study to Evaluate the Feasibility of CPI-613 Given with High Dose Cytarabine and Mitoxantrone in Patients with Relapsed or Refractory Acute Myeloid Leukemia (AML)

NCT Clinicaltrials.gov: NCT02484391

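### The exploratory response comparison uses one crude historical rate of 41% and ignores cytogenetic risk, so a systematic difference in poor-risk share from the historical cohort would bias it

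*Combined protocol and SAP*

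**What the plan says.** The exploratory paragraph of Section 10 (Analysis Plan) compares complete response and 60-day mortality with a named historical cohort (22111), overall and by dose. For response, "In the historical cohort the response rate was estimated to be 41" per cent. The test is set out as "Using a one-sided chi-square test, a 0.05 significance level, null hypothesis of 41%, and assuming 70% power", and improvement could be shown "if we are able to achieve a response rate of 56% or higher". For mortality, "Early mortality in the historical cohort was estimated to be 29% at 60 days", with a corresponding exact test. The paragraph mentions no stratification, standardisation or adjustment. It gives neither the size nor the risk mix of the historical cohort.

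Section 1.4 argues for the regimen within a cytogenetic stratum: "In this trial patients with poor risk cytogenetics had a 46% response rate, far superior to the 19% response seen with historical data".

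Under "Cytogenetics at Diagnosis", the pre-study form in Appendix D records the risk category as Good, Intermediate, Poor, Unknown or Not Done. Section 10 does not refer to this variable.

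Section 5.3 states that dose assignment is not randomised.

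**The concern.** A one-sample test against 41% asks whether the trial's response rate exceeds 41%. That equals asking whether CPI-613 improves response only if patients like those in this trial would have responded at 41% without it. The protocol's own rationale indicates that historical response varies widely with cytogenetic risk. The rate expected with no drug effect therefore depends on how many poor-risk patients this trial enrols.

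Nothing in the design ties that share to the historical one. If the trial has fewer poor-risk patients, the crude test can credit case mix to the drug. If it has more, the test can miss a real gain. The result would not alter the feasibility decision, but Section 10 attaches a formal significance level and a threshold to it. It could reasonably be read as evidence for taking the regimen into larger trials, which Section 5.3 gives as the purpose of the study.

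**Working it through.** **Inputs from the documents.** Null response 41%, alternative 56%, one-sided 0.05, 70% power (Section 10, exploratory paragraph). Poor-risk historical response 19% (Section 1.4). N = 60, taken from the precision statement in Section 10, because the exploratory paragraph gives no N.

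**Assumptions, not in the documents.** The 19% and the 41% come from the same cohort and use the same response definition. The historical poor-risk share *h* lies between 0.2 and 0.5. The trial share *t* differs from it by 10 points.

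**Step 1: reproduce the plan's figure.** With X ~ Binomial(60, p), the exact rule that keeps the level at or below 5% is success if X ≥ 32.
- P(X ≥ 32 | 0.41) = 3.6%
- P(X ≥ 32 | 0.56) = 70.9%

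The plan's 56% at 70% power therefore reproduces at N = 60. The arithmetic is sound, and the issue is the fixed null.

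The chi-square test without continuity correction would already reject at 31/60: z = (31/60 − 0.41)/√(0.41 × 0.59/60) = 1.68, above 1.645. The exact false-positive rate at that cut-off is 6.2% with no shift at all. I use 32/60 so that none of the inflation below comes from the normal approximation.

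**Step 2: response expected with no drug effect.** The historical rate in patients who are not poor risk is r = (0.41 − 0.19h)/(1 − h). The expected rate in the trial is p(t) = 0.19t + (1 − t)r. For example, with h = 0.3, r = (0.41 − 0.057)/0.7 = 50.4%. With t = 0.2, p = 0.19 × 0.2 + 0.8 × 0.504 = 44.1%. In general, a 10-point shift moves the null by 0.10 × 0.22/(1 − h).

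**Step 3: error rates with the fixed 32/60 rule.** The false-positive rate is P(X ≥ 32 | p). Power is P(X ≥ 32 | p + 0.15).

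| h | r | t = h − 0.10: no-effect rate | False positives | t = h + 0.10: no-effect rate | Power for +15 points |
|---|---|---|---|---|---|
| 0.2 | 46.5% | 43.75% | 8.6% | 38.25% | 54.7% |
| 0.3 | 50.4% | 44.1% | 9.7% | 37.9% | 52.3% |
| 0.4 | 55.7% | 44.7% | 11.1% | 37.3% | 49.1% |
| 0.5 | 63.0% | 45.4% | 13.5% | 36.6% | 44.5% |
| No shift | – | 41% | 3.6% | 41% | 70.9% |

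**The case against.** The strongest reply is that only a systematic difference in risk mix matters, and the documents show none. If patients were drawn from a population with the historical mix, each response would be Bernoulli with probability 0.19h + (1 − h)r = 0.41. Chance variation in mix is then already inside the binomial variance and the test keeps its level. This is correct. The table describes what a shift would do and is not evidence that one exists.

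It is also true that the link between the two historical figures is assumed. Section 1.4 attributes the 19% only to historical data, while Section 10 names cohort 22111 for the 41%. The definitions may differ too: Section 1.4 reports an overall rate that combines complete remission with and without full count recovery, while the exploratory paragraph speaks first of complete response and then of response rate. And the comparison is labelled exploratory.

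Three stronger readings are tempting but unsupported:

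- **That the by-dose tests suffer most.** A reader might infer this from the small dose groups. Chance imbalance does not break the test's level, and a given shift does less to it at n = 20. With h = 0.3 and t = 0.15, the no-effect rate is 0.19 × 0.15 + 0.85 × 0.504 = 45.7%. The false-positive rate is then 6.6% at n = 20 (cut-off 13/20, 2.6% unshifted), against 14.6% at n = 60.
- **That the mortality comparison is biased in the same way.** No risk-specific 60-day mortality appears anywhere. If mortality did not vary with cytogenetic risk, case mix would not affect the 29% null.
- **That this trial's entry criteria select fitter patients than the historical cohort.** The historical cohort's criteria are not given, so this cannot be checked.

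What remains is that the plan tests against a crude rate, cites a much lower rate in one risk stratum, collects that stratum, and does not use it.

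**Conclusion.** The concern holds for the exploratory response comparison. A systematic 10-point difference in poor-risk share is enough to raise the false-positive rate from 3.6% to about 9–14%, or to lower power for a true 15-point gain from 71% to about 45–55%, depending on its direction.

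These figures rest on a common source and definition for the 19% and the 41%, an assumed historical poor-risk share of 20–50%, and N = 60. If the two figures come from different cohorts, the size changes. The crude null would still ignore a factor that the protocol itself uses to argue for efficacy.

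No bias has been shown to exist, and none is claimed for mortality or specifically for the by-dose tests. The consequence is for interpreting an exploratory result; the primary feasibility conclusion does not depend on it. The change should be made because it is cheap and relies on a baseline variable already collected in this trial.

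**What to change.** In Section 10:

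1. Make the main exploratory response comparison one against the historical rate directly standardised to this trial's mix: the sum over poor and not-poor groups of trial share × historical response in that group. If patient-level data from cohort 22111 are available, use instead a Mantel-Haenszel risk difference with a 95% confidence interval, stratified by the same two groups.
2. State the source and the response definition of the 19% and the 41%, and use one definition throughout the comparison.
3. Report the cytogenetic risk mix of both cohorts.
4. Specify how Unknown and Not Done are handled, either as a separate category or in a sensitivity analysis.
5. Keep the crude test against 41% as secondary.
6. Do the same for 60-day mortality only if historical rates by risk group exist.

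Keep to the single poor versus not-poor split. Adding age, with a category for unknown risk, would give too many strata for cohorts of 20.

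The cost is a few sentences of plan text and a small extra analysis, with no new patients, visits or data collection in this trial. It does require the historical cohort's response by risk group, and the interval will be slightly wider.

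### The 16.8% mortality figure is the true rate detectable with 70% power at N = 60, not the rate that must be observed; the exact test already rejects at 11/60 (18.3%)

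*Combined protocol and SAP*

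**What the plan says.** The last paragraph of the Analysis Plan in Section 10.0 describes exploratory comparisons of complete response and 60-day mortality with a historical cohort, overall and by dose.

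- **Mortality.** The reference value is given first: "Early mortality in the historical cohort was estimated to be 29% at 60 days". The test follows: "We will use a one-sided exact test for a single proportion, a 0.05 significance level, a null hypothesis of 29%, and 70% power". The paragraph then concludes that, to show a significant decrease, "we would need to observe a 60 day mortality rate of 16.8% or lower".
- **Response.** The test is introduced with "Using a one-sided chi-square test", at the 0.05 level, with a null of 41% and 70% power. The plan then states that "we would be able to show significant improvement in response if we are able to achieve a response rate of 56% or higher".
- **Sample size.** This paragraph gives none. The Analysis Plan uses 60 twice before it: "if we enroll 60 patients" for feasibility and "Assuming a response rate of 0.5, with 60 participants" for the response interval. The opening of Section 10.0 plans accrual "for a total of 67 patients". The two totals differ by the 7 patients already treated at 2,500 mg/m²: 20 + 20 + (17 + 3) = 60 at the three doses under study, and 60 + 7 = 67.

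**The concern.** The rate that must be observed for significance is a rejection boundary. It depends on N, the null rate and alpha. Power does not enter it. A figure obtained by also specifying 70% power is a true rate under the alternative, and the boundary on the observed rate is less extreme than that. The mortality sentence combines the two: it takes a figure derived from power and presents it as what must be observed.

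If that is so, the plan supports two opposite statements about the same data. A reader who compares the observed rate with 16.8% would call some results non-significant that the named test declares significant. Because the sentence carries no N and the comparison is also planned by dose, the same figure could be applied to groups of 20, where it would err in the other direction.

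**Working it through.** **Inputs**, all from Section 10.0: null 60-day mortality 0.29; one-sided exact binomial test; alpha 0.05; power 0.70; N = 60 (used twice in the Analysis Plan), with N = 67 (total accrual) as the alternative.

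**Method.** Find the largest count c with P(X ≤ c | N, 0.29) ≤ 0.05. The observed cut-off is c/N. Then solve P(X ≤ c | N, p) = 0.70 for p, the true rate detectable with 70% power.

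**Step 1: observed cut-off at N = 60**

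| Deaths | Observed rate | P(X ≤ deaths), true rate 0.29 |
|---|---|---|
| 10 | 16.7% | 0.0208 |
| 11 | 18.3% | 0.0423 |
| 12 | 20.0% | 0.0782 |

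Hence c = 11 and the observed cut-off is 11/60 = 18.3%.

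**Step 2: reproduce the plan's figure.** Solving P(X ≤ 11 | 60, p) = 0.70 gives p = 0.1677, which rounds to the printed 16.8%. Power at a true rate of exactly 0.168 is 0.698. The number is therefore right as a true rate at N = 60.

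**Step 3: can another N rescue the wording?** Over every N from 20 to 119, no observed cut-off c/N rounds to 16.8%. The 70%-power true rate rounds to 16.8% only at N = 60 (0.1677) and N = 71 (0.1680). This supports N = 60 as the number behind the figure. At N = 67, P(X ≤ 12) = 0.0271 and P(X ≤ 13) = 0.0512, so the cut-off is 12/67 = 17.9%, and the 70%-power true rate is 16.4%.

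**Step 4: cost of reading 16.8% as a threshold at N = 60.** An observed rate of 16.8% or lower allows at most 10 deaths.

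| Rule | Size at 29% | Power at a true 16.8% |
|---|---|---|
| Named test, ≤ 11/60 | 4.2% | 70% |
| Printed threshold, ≤ 10/60 | 2.1% | 57% |

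The two rules differ only at exactly 11 deaths, which has probability 0.126 when the true rate is 16.8%.

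**Step 5: a single dose group, n = 20.** P(X ≤ 2) = 0.0433 and P(X ≤ 3) = 0.1256, so the cut-off is 2/20. A result of 3/20 = 15% lies below 16.8% but is not significant.

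**Step 6: the response figure (null 0.41).** For x responders, the uncorrected statistic is z = (x − 0.41N)/√(N × 0.41 × 0.59). The corrected version subtracts a further 0.5 from the numerator.

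- N = 60, uncorrected: 31/60 gives z = 1.68, p = 0.046; 30/60 gives p = 0.078. The cut-off is 31 (51.7%).
- N = 60, continuity-corrected: 32/60 gives z = 1.81, p = 0.035; 31/60 gives p = 0.061. The exact test gives 0.036 and 0.062. The cut-off is 32 (53.3%) for both.
- N = 60, true rate with 70% power: 0.558 exact; 0.556 corrected (normal approximation); 0.542 (binomial) or 0.548 (normal approximation) uncorrected. So 56% fits the corrected or exact version as a detectable true rate.
- N = 67: the cut-off is 35 (52.2%) for all three versions (p = 0.031, 0.040 and 0.041 for uncorrected, corrected and exact).

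**The case against.** The strongest reply is that nothing is miscalculated and that the finding turns on one verb. The sentence before states the power, so a statistical reader will recognise a design alternative. The plan decides significance by the named exact test, and an analyst who runs it gets the right answer. At N = 60 the printed figure and the test disagree only at 11 deaths. The 12.6% chance of that result is quoted near its peak: it is 10.3% at a true mortality of 15%, 6.2% at 25% and 2.2% at the null of 29%. The printed reading is the stricter one at both N = 60 and N = 67, so it cannot create a false claim of benefit at study level. The comparison is exploratory and is neither a primary nor a secondary objective.

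All of this stands, and it limits the weight of the point. It does not make the sentence true: the sentence states a condition for significance that the test named just before it does not impose. The response sentence differs, because a rate to be achieved can be read as a true rate; that one is ambiguous, not wrong. The claim that the error is always conservative fails if the figure is carried over to a dose group, where 3/20 would pass 16.8% with p = 0.126. The plan states no by-dose threshold, so that remains a risk of misuse and is not a second error in the text.

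**Conclusion.** The mortality sentence is wrong as written. At N = 60 the observed cut-off is 11 deaths (18.3%), 1.5 percentage points above the printed 16.8%, which is the true rate detectable with 70% power. N = 60 is inferred, because the paragraph gives no N, but it agrees with the rest of the Analysis Plan and is the number at which 16.8% reproduces. The conclusion that 16.8% is not an observed cut-off does not depend on this choice, since it holds for every N from 20 to 119. The consequence is modest: one possible result out of 60 patients is misclassified, in the conservative direction, in an exploratory analysis. The primary feasibility conclusion is unaffected. It should be corrected because a significance threshold written into the plan ought to agree with its own test.

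**What to change.** 1. Describe 16.8% as the true 60-day mortality at which the test has 70% power, state the N, and add the observed cut-off. For N = 60: 11 or fewer deaths (18.3%). If all 67 patients are to be analysed: 12 or fewer deaths (17.9%), with 16.4% replacing 16.8%.
2. Describe 56% in the same way, as a detectable true response rate, and say which version of the chi-square test is meant. If an observed cut-off is printed, give it for that version. For N = 60: at least 31 responders uncorrected, or at least 32 corrected or exact. For N = 67: at least 35.
3. Add a sentence that these are study-level figures and do not carry over to the by-dose comparisons; at n = 20 the exact mortality cut-off is 2 deaths.

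The cost is two reworded sentences and a few added figures in one paragraph. The design, sample size and named tests do not change.
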